6.2 Design

Although the hypothesis of the study has been based on various congruent information that allow us to face with sufficient guarantee the feasibility of the study and the eventual demonstration of the virological and immunological efficacy of the ATRIPLA® dose reduction strategy, we are not absolutely certain that an unacceptably high virological failure rate (standard viral load ≥ 37 copies/mL on two consecutive occasions) can occur in the arm

experimental. We will consider a priori that the failure of at least 20% (n=6) of the patients in the experimental arm will represent an unacceptably high virological failure rate. In this case, its conclusion will be considered premature. In this extreme case, the data of the patients already included up to the time of the premature conclusion of the study would be analyzed.

The present study is proposed as a proof of concept to be able to formulate another study with a sufficiently large sample size to adequately demonstrate the non-inferiority of the strategy. The results of the present study can help to design the non-inferiority study and to estimate its sample size.

STUDY PROCEDURES

Selection Evaluations								
Clinical Evaluations		Selection						
Informed consent								X
Inclusion and exclusion criteria								X
Assignment of the selection code								X
Vital signs								X
Weight Determination								X
Height determination								X
Demographics								X
Medical history								X
Physical examination								X
Concomitant medications								X
Confirmation of the use of contraceptive methods by the patient and his or her partner								X

Clinical Evaluations	Basal Day 0	S 1 (#)	S 2 (#)	S 4 (#)	S 6 (#)	S 8 (#)	S 12	S 24
Meet Inclusion and Exclusion Criteria	X							
Signed Informed Consent	X							
Vital signs	X							
Weight	X							X
Physical examination	X						X	X
Adverse events		X	X	X	X	X	X	X
Concomitant medications	X	X	X	X	X	X	X	X
Simplified Compliance Questionnaire		X	X	X	X	X	X	X
Test sobre calidad del sueño (Pittsburgh Sleep Quality Index)	X							X
Haematology	X							X
Blood biochemistry	X							X

Clinical Evaluations	Basal Day 0	S 1 (#)	S 2 (#)	S 4 (#)	S 6 (#)	S 8 (#)	S 12	S 24
Standard plasma viral load	X	X	X	X	X	X	X	X
Ultrasensitive plasma viral load (\$)	X							X
HIV-1 reservoir of PBMCs	X							X
Immunology (CD4/CD8)	X						X	X
Immunology Sample	X							X
Pregnancy test (women only) Y(&)	X	X	X	X	X	X	X	X
Pharmacokinetics	X							X

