8.1 Treatment Branches

Randomization to two treatment groups: A or B

GROUP A (control): ATRIPLA® at standard daily dose (1 tablet daily) for a period of 24 weeks

GROUP B (experimental): ATRIPLA® at a dose three days per week (1 tablet Monday, Wednesday and Friday) for a period of 24 weeks

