11.1 Sample

The study will be carried out in 60 patients. This is a proof of concept and does not require an ad-hoc sample size calculation.

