11.2 Sample size

11.3 Analysis

Comparison of patient proportions will be performed using Fisher's exact test and the 95% confidence interval will be calculated for the difference in proportions.

Quantitative data at baseline and after 24 weeks, as well as absolute and relative changes at 24 weeks, will be compared using the Wilcoxon rank sum test. The point estimate and 95% confidence interval of the difference in medians will be estimated using the Hodges-Lehman methodology using the Moses free distribution.

Correlations between continuous variables will be evaluated using Spearman's rank correlation test.

The study of baseline predictors of response will be carried out by means of a multivariate analysis of multiple logistic regression.

Limitations of the study:

Although the hypothesis of the study has been based on various congruent information that allow us to face with sufficient guarantee the feasibility of the study and the eventual demonstration of the virological and immunological efficacy of the ATRIPLA® dose reduction strategy, we are not absolutely certain that an unacceptably high virological failure rate (standard viral load ≥ 37 copies/mL on two consecutive occasions) may occur in the experimental arm. We will consider a priori that the failure of at least 20% (n=6) of the patients in the experimental arm will represent an unacceptably high virological failure rate. In this case, its conclusion will be considered premature. In this extreme case, the data of the patients already included would be analyzed.

This study, even with the most favorable virologic and immunological results, would not constitute definitive proof of the safety and efficacy of ATRIPLA®'s dose reduction strategy. The present study is only a proof of concept and another study with a sufficiently large sample size would be needed to adequately demonstrate the non-inferiority of the strategy. The results of the present study can help to design the non-inferiority study and to estimate its sample size.

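### If response in 11.3 means viral load <37 copies/mL, failures will probably be too few for ordinary multiple logistic regression; the endpoint, arms, number of terms and a sparse-event method should be stated.

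*Combined protocol and SAP*

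**What the plan says.** On predictors, section 11.3 has one sentence: "The study of baseline predictors of response will be carried out by means of a multivariate analysis of multiple logistic regression". It does not define response, name or limit covariates, say whether one or both arms are modelled, or provide for sparse events.

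On size, section 11.1 says "The study will be carried out in 60 patients" and "This is a proof of concept and does not require an ad-hoc sample size calculation". Section 8.1 gives "Randomization to two treatment groups: A or B" without a ratio.

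Sections 6.2 and 11.3 treat "failure of at least 20% (n=6) of the patients in the experimental arm" as unacceptably high. The event counted there is "standard viral load ≥ 37 copies/mL on two consecutive occasions". The consequence is "In this case, its conclusion will be considered premature", and the data on patients already included would still be analysed.

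The primary endpoint (1.13.1 and 6.1) is a viral load <37 copies/mL at week 24 by intention to treat, which is not the same event as confirmed failure. The list in 1.13.2 uses the word response only for <1 copy/mL. Section 11.5 rules out imputation and analyses available data. Section 10.4 states that no interim analysis is planned.

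**The concern.** Logistic regression draws its information mainly from the rarer outcome. Here that is likely to be failure. The patients have at least two years of suppression (7.1) and no previous virologic failure or relevant mutations (7.2), and the trial is meant to conclude early if six experimental patients fail.

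With so few events, maximum likelihood has two problems. If all failures fall in one level of a binary covariate, the estimate is infinite. If they do not, the estimate is finite but very variable, and biased away from 1 when there is a real effect. Either way, a chance imbalance can look like a strong predictor.

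The stake is limited but real. Sections 6.2 and 11.3 say that the results may help to design the non-inferiority study, and a spurious predictor would be an unhelpful input to it. The comparison of proportions already uses Fisher's exact test. The regression has no comparable small-sample provision.

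**Working it through.** **1. The plan's own figure.** The total is 60 (11.1). Equal allocation is an assumption, implied by the rule: 0.20 × 30 = 6, which reproduces n=6. The smallest whole number at or above 20% is 6 for any arm size from 26 to 30. A trial that does not meet the rule therefore has at most 6 − 1 = 5 confirmed experimental failures.

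**2. Likely number of events.** The only suppression rate in the documents is 90%, from the earlier 30-patient study of a different schedule (section 4), a failure rate of 10%. Other rates are assumptions. For a binomial count with n = 30:
- 10%: expected 30 × 0.10 = 3.0; P(0 or 1) = 0.9^30 + 30 × 0.1 × 0.9^29 = 0.042 + 0.141 = 18%; P(6 or more) = 7%.
- 5%: expected 1.5; P(0 or 1) = 0.215 + 0.339 = 55%.
- 2%: P(0) = 0.98^30 = 55%, and no model can be fitted.

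Five events give 5/2 = 2.5 events per covariate with two covariates and 5/4 = 1.25 with four.

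**3. One binary covariate, 30 patients.** With m patients in one level and E failures, P(all failures in one level) = [C(m,E) + C(30−m,E)] / C(30,E), for E of 2 or more.
- E = 5, m = 15: 2 × 3,003 / 142,506 = 4%. With m = 6: (6 + 42,504) / 142,506 = 30%.
- E = 3: 22% (m = 15) and 50% (m = 6).
- E = 2: 48% (m = 15) and 67% (m = 6).
- E = 1: always.

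**4. Several noise covariates.** Each setting has 500 simulated data sets, so the Monte Carlo standard error is at most √(0.25/500) = 2.2 percentage points. Covariates are independent: half standard normal, half binary with the prevalence shown. Extreme means that some odds ratio is above 5 or below 0.2.

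| N | Failures | Covariates (binary prevalence) | ML infinite | ML finite but extreme | Either | Firth extreme |
|---|---|---|---|---|---|---|
| 30 | 3 | 2 (50%) | 22% | 7% | 28% | 24% |
| 30 | 3 | 4 (50%) | 41% | 18% | 59% | 43% |
| 30 | 3 | 4 (20%) | 78% | 11% | 89% | 30% |
| 30 | 5 | 2 (50%) | 5% | 24% | 29% | 8% |
| 30 | 5 | 4 (50%) | 8% | 42% | 50% | 18% |
| 30 | 5 | 4 (20%) | 51% | 19% | 70% | 28% |

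With both arms pooled (N = 60), the range for either problem is 12% to 63% at five failures, 11% to 41% at seven and 4% to 23% at ten. At 20 non-responders it is 1% to 9%, and at 30 it is 0% to 6%.

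**5. A real effect.** With N = 30, five failures, four covariates (binaries about 50%) and a true odds ratio of 2, ML is infinite in 15% of data sets. The 10th, 50th and 90th percentiles of its finite estimates are 1.15, 2.56 and 12.1. Firth is always finite: 1.08, 1.96 and 4.6.

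**6. Arm in the model.** If there are experimental failures but no control failures, the arm odds ratio is infinite. The chance of no failures among 30 controls is 0.99^30 = 74% at an assumed 1% control failure rate and 0.95^30 = 21% at 5%.

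**The case against.** The strongest objection concerns the outcome. The only endpoint that the plan calls a response is <1 copy/mL, and its rate is not given. With 20 to 30 non-responders among 60, the instability nearly disappears. This stands, and it is why the point is conditional and why the first request is to name the endpoint.

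A reader might infer that a completed trial can have no more than five failures. The documents do not support that. The rule counts confirmed failures in the experimental arm only. Control failures and single week-24 values of 37 or more are outside it. So are missing values, if intention to treat is taken to count them as failures, which 11.5 leaves open. With no interim analysis planned, a sixth failure could also appear at the last visits.

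A reader might also infer that the planned model must give infinite odds ratios. It need not. With normally distributed covariates and no arm term, ML fails to give an estimate in only 0% to 3% of data sets at three to five failures. The infinite arm estimate requires arm in the model and no control failure, and the plan mentions only baseline predictors.

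Nor is multiple regression the main cause of the instability. With 60 patients and normal noise covariates, a given covariate had an odds ratio above 2 or below 0.5 in 33%, 26% and 21% of data sets at three, four and five failures when three covariates were fitted, and in 28%, 22% and 17% when it was fitted alone. Wald p < 0.05 occurred in only 1.6% to 4.3%, so intervals would usually show these odds ratios to be uninformative. This stands, and one-at-a-time reporting should therefore be descriptive.

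Finally, predictors of response appear in no objective or endpoint, and the trial is a proof of concept. That lowers the severity. It does not remove the point: covariates are left open, binary ones are likely among baseline characteristics, and with two normal covariates and one binary of 30% prevalence, ML was non-estimable in 35% to 39% of data sets at three failures and in 17% to 18% at five.

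**Conclusion.** The concern holds in conditional form. For the <37 copies/mL outcome, the n=6 rule and the one cited suppression rate point to few events, so ordinary multiple logistic regression is likely to give unstable odds ratios. Infinite ones become likely when a covariate is an uncommon binary, or when arm is modelled and no control patient fails. Five failures is the most favourable count under the cap, and fewer are more likely at the cited 10% rate. For <1 copy/mL the concern may not arise.

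The figures rest on 30 patients per arm, independent covariates and assumed prevalences, none of which the plan states. Severity is minor: the analysis is exploratory, and the primary comparison by Fisher's exact test with a confidence interval is unaffected.

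**What to change.** In 11.3:
- State which endpoint response refers to and which arms are modelled.
- For the <37 copies/mL outcome, replace ordinary maximum likelihood by Firth-penalised logistic regression with profile-likelihood intervals, or by exact logistic regression. Allow at most one or two pre-named terms, including arm.
- Report all other predictors descriptively, one at a time.
- Label the analysis exploratory.

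The cost is a few sentences, and the methods are in standard software. The downside is that fewer predictors can be examined jointly. Firth's penalty removes infinite estimates and reduces small-sample bias, but it does not make about five events informative: in the four-covariate settings above it still gave an extreme odds ratio in 18% to 28% of null data sets at five failures. The limit on terms and the exploratory label are therefore needed as well as the penalty.

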11.4 Completion Criteria

The study will be considered to have been completed on the date of the last visit of the last subject recruited into the study.

11.5 Processing of lost data

Missing data imputation techniques will not be used. Only the available data will be analyzed.

11.6 Deviations from the statistical plan

Any deviation from the planned statistical analyses will be justified and detailed in the reports derived from the processing of the data.

11.7 Population under analysis

The population analyzed in the study will consist of all patients included in the study as detailed in the protocol and without major deviations from the protocol.

12. Direct Access to Source Data/Documents

The sponsor shall ensure that it is specified in the protocol or other written agreement that the investigator or institution shall allow direct access to the source data or documents for monitoring, auditing and review by the IRB as well as inspection of the trial by the competent health authorities.

13. Ethics

General considerations: The test will be carried out in accordance with the principles emanating from the Declaration of Helsinki (See Annex *VIII*) and according to the legal regulations in force (Royal Decree 223/2004) and will not be started until the approval of the reference IRB has been obtained, the

approval of the Management of all participating centres, and authorisation from the Spanish Agency for Medicines and Health Products.

Information to the subjects: Patients will be informed orally and in writing and all relevant information adapted to their level of understanding will be communicated to the participants.
(See *Attachment III: Patient Information Sheet/Written Consent Sheet*)

14. Data Management and Records Archiving

The patient will be informed that their participation in the trial will be treated with the same confidentiality as their clinical documentation.

In the data collection notebook, the patient will be identified only by their inclusion code in the study.

The patient's name will not appear in any publication or communication of the results of the study.

The patient's participation in the trial will be reflected in their medical history.

The investigator will complete a list that will include the names of the patients participating in the trial, their inclusion number in the trial and their medical history.

Only researchers and data quality assurance and data analysis personnel will have access to the participant's clinical documentation. Eventually, persons duly authorised by the Sponsor and the Health Authorities and the Clinical Research Ethics Committee may audit or inspect the trial. Personal information will not be available to the public, in compliance with the provisions of Organic Law 15/1999, of 13 December, on the Protection of Personal Data.

Prior to the start of treatment, a clinical examination, electrocardiogram and blood and urine sample will be taken (*SEE TABLE OF DAILY DETERMINATIONS*).

The data will be collected through an online electronic CRD.

15. Financing & Insurance

The promoter has taken out civil liability insurance in accordance with current regulations.

16. Publication Policy

The Promoter undertakes to publish the results, both positive and negative, of this study as stated in art. 39 of RD 223/2004.

17. Table of Examinations and treatment during follow-up

Selection Evaluations		Selection
Clinical Evaluations		
Informed consent		X
Inclusion and exclusion criteria		X
Assignment of the selection code		X
Vital signs		X
Weight Determination		X
Height determination		X
Demographics		X
Medical history		X
Physical examination		X
Concomitant medications		X
Confirmation of the use of contraceptive methods by the patient and his or her partner		X

Clinical Evaluations	Basal Day 0	S 1 (#)	S 2 (#)	S 4 (#)	S 6 (#)	S 8 (#)	S 12	S 24
Meet Inclusion and Exclusion Criteria	X							
Signed Informed Consent	X							
Vital signs	X							
Weight	X							X
Physical examination	X						X	X
Adverse events		X	X	X	X	X	X	X
Concomitant medications	X	X	X	X	X	X	X	X
Simplified Compliance Questionnaire		X	X	X	X	X	X	X
Test sobre calidad del sueño (Pittsburgh Sleep Quality Index)	X							X
Haematology	X							X
Blood biochemistry	X							X
Standard plasma viral load	X	X	X	X	X	X	X	X
Ultrasensitive plasma viral load (\$)	X							X
HIV-1 reservoir of PBMCs	X							X
Immunology (CD4/CD8)	X						X	X
Immunology Sample	X							X

Clinical Evaluations	Basal Day 0	S 1 (#)	S 2 (#)	S 4 (#)	S 6 (#)	S 8 (#)	S 12	S 24
Pregnancy test (women only) Y(&)	X	X	X	X	X	X	X	X
Pharmacokinetics	X							X

All laboratory specimens should be obtained prior to administration of the first dose of study medication.

(#) These visits will be made only to patients who are in the experimental treatment arm (3-day-per-week treatment)

& At baseline visit it is advised to perform a blood pregnancy test

* Genotypic resistance testing will be performed if the patient has virologic failure (defined by HIV-1 plasma viral load >50 copies/mL confirmed on two consecutive occasions)

Blood biochemistry: lipids (TG, total cholesterol and HDL), creatinine and estimated glomerular filtration rate (CPK-EPI), levels of 25OH vitamin D.

Hematology: Blood count

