6.1 Primary and Secondary Endpoints**Primary Endpoint:**

The primary endpoint of the study will be the proportion of patients who continue to have a standard plasma viral load (<37 copies/mL) at 24 weeks by intention-to-treat analysis.

Secondary endpoints:

- 1) The proportion of patients with ultrasensitive viral load (<1 copy/mL) after 24 weeks.
- 2) The change from baseline to 24 weeks in the viral reservoir of peripheral blood mononuclear cells
- 3) Changes from baseline to 24 weeks in TREC production, immune profile of activation (CD38 and HLA-DR) and senescence (CD57 and CD28) in CD4 and CD8 lineages, in naïve and effector and memory T cell ratios (CCR7 and CD45RA), and changes in apoptosis levels in vitro by annexin V staining.
- 4) Changes in plasma levels of efavirenz.
- 5) Changes in sleep quality (Pittsburgh Sleep Quality Index), plasma levels of vitamin D and lipids, and estimated glomerular filtration rate.
- 6) Overall safety (reporting side effects, serious side effects, and discontinuation of treatment due to side effects)

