10.1 Detection and recording of Adverse Events

It is the investigator's responsibility to detect and document any event that meets the criteria and definitions of adverse event (AE) or serious adverse event (SAE) as set forth in this protocol. During the study, the existence of adverse events, whether serious or not, will be checked in accordance with the definition given in this section of the protocol.

a) Minimum information to be specified:

Description/definition:

Adverse event (AE) is any adverse health event in a patient or clinical trial subject treated with a medicine, even if it is not necessarily causally related to that treatment. Therefore, it can be any unfavorable and unintended signs (including an abnormal laboratory finding), symptom, or illness temporarily associated with the use of an investigational drug, whether or not related to the investigational drug.

Laboratory abnormalities of clinical importance that meet one or more of the following criteria are also considered AEs:

- It requires additional intervention or treatment.
- Requires a modification of the dose.

- It is accompanied by a clinical manifestation.

Any analytical anomaly that the investigating physician considers to be of clinical importance must be recorded as such in the printed copy of the laboratory report, indicating the physician's initials and the date of revision. An AA is also considered to be any event associated or observed in conjunction with an accidental or intentional overdose of the product, or with abuse or withdrawal of the product.

All AEs will be recorded in the subject's medical record and in the eCRDe. The start and end dates of each AA, the intensity and the relationship with the study drug will be recorded.

The criteria for subject treatment, dose discontinuation, dosage adjustment, withdrawal, or treatment changes will only apply to toxicities attributable to the study drugs (i.e., efavirenz, tenofovir, and emtricitabine).

The classification system for drug toxicity is set out in the DAIDS Table for Grading the Intensity of Adverse Events in Adults and Children, which can be found on the DAIDS RSC website: <http://rsc.tech-res.com/safetyandpharmacovigilance/>.

In addition, for each AA, the measures taken or the outcome (e.g. hospitalization, discontinuation of treatment) will be recorded.

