10.2. Notification

The investigator or designee **must notify all AAGs, regardless of whether or not they are considered drug-related or planned**, to the head of the CTU. [name] ([contact]) [contact] [name] [REDACTED] in order to notify local and national health authorities **within one working day of becoming aware of the event**, so that the contact of the designated promoter can prepare the corresponding written report. AAGs occurring will be reported at any time from the subject's inclusion in the study and up to 30 days after the study has been completed or discontinued. In the specific case of selection failure, the AAGs will be recorded from the moment the consent is signed until the subject is considered a selection failure.

Regardless of the classification of adverse effects, the Investigator must collect all the AEs in the corresponding section of the study data collection notebook (CRD) and fill in all the information pertaining to them.

The sponsor must notify in an EXPEDITIOUS manner all relevant SAFETY INFORMATION, i.e. that could modify the risk/benefit ratio of the investigational medicine, or determine changes in its administration schedule or in the conduct of the trial, for example:

- a qualitative change or an increase in the percentage of occurrence of expected RAGs, which is considered clinically important.
- RAGIs that occur after the completion of a clinical trial and that are notified by the investigator to the sponsor.
- New developments related to the conduct of the trial or the development of the investigational medicinal product and likely to affect the safety of the subjects, such as:
 - Serious adverse events that may be associated with the trial procedures and may modify the conduct of the trial
 - A significant risk to subjects such as the lack of efficacy of an investigational drug used for the treatment of a life-threatening disease.
 - Important new safety findings from new animal studies (such as cardiogenicity).
 - Any premature termination or temporary halt of a clinical trial with the same investigational medicinal product for safety reasons, carried out in another country and by the same sponsor.
 - GRAs related only to an MNI that are considered relevant as they are not subject to RAGI's general rules of expedited reporting of individual cases.
- Any recommendations from the data monitoring committee, which are relevant to the safety of the subjects.

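### Section 11.7 leaves patients with major deviations out of the only defined analysis population, and overall safety has no population of its own, so the safety comparison can be biased

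*Combined protocol and SAP*

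**What the plan says.** Section 11.7 is the only place in the statistics chapter that defines who is analysed: "The population analyzed in the study will consist of all patients included in the study as detailed in the protocol and without major deviations". It makes no exception for safety and does not say what counts as major.

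Section 6.1 defines the primary endpoint as the "proportion of patients who continue to have a standard plasma viral load (<37 copies/mL) at 24 weeks by intention-to-treat analysis". Intention-to-treat is mentioned for that endpoint and for no other. Secondary endpoint 6 in the same section reads "Overall safety (reporting side effects, serious side effects, and discontinuation of treatment due to side effects"; it names no population.

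The safety chapter requires complete collection. Section 10.1 states "All AEs will be recorded in the subject's medical record and in the eCRDe". Section 10.2 adds that "the Investigator must collect all the AEs in the corresponding section of the study data collection notebook (CRD", and on serious events says "AAGs occurring will be reported at any time from the subject's inclusion in the study and up to 30 days after the study has been" (the sentence ends by naming completion or discontinuation). These are duties to record and notify. Neither section defines a set of patients for the safety analysis.

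**The concern.** General tolerability is a stated objective (sections 1.10.2 and 5), and lower toxicity is part of the rationale in section 4. The results are also meant to inform a larger non-inferiority trial (sections 6.2 and 11.3). A safety comparison is normally made in everyone exposed, because departing from the protocol can itself result from an adverse event. A patient who feels unwell may skip tablets, change schedule or miss a visit. If that patient is then classed as a major deviator, the event disappears from the endpoint together with the patient.

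Three features of this trial make the exclusion hard to defend. Major is undefined. The study is open-label, so the classification can be made knowing both the arm and the event. And compliance is checked far more often in one arm than in the other, so deviations may be found unequally. With arms this small, a few exclusions can change the picture of tolerability.

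**Working it through.** **Which population governs endpoint 6**

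1. Section 11.7: the population analysed in the study excludes patients with major deviations.
2. Section 6.1: intention-to-treat applies to the primary endpoint, and endpoint 6 has no population.
3. Sections 10.1 and 10.2: all adverse events are recorded and serious ones notified, with no analysis set defined.
4. Section 11.6: any departure from the planned analyses must be justified and detailed.

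So 11.7 applies to endpoint 6 by default. An analyst who sensibly included every treated patient would have to report this as a departure from the plan.

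**How often deviations can be found**

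In the visit table (sections 6.2 and 17), the compliance questionnaire falls at weeks 1, 2, 4, 6, 8, 12 and 24. Weeks 1 to 8 are marked as experimental arm only. That gives 7 post-baseline checks in the experimental arm and 2 (weeks 12 and 24) in control.

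**Arm size**

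- Section 11.1: "The study will be carried out in 60 patients. This is a proof of concept and does not require an ad-hoc sample size calculation".
- Section 11.3: "failure of at least 20% (n=6) of the patients in the experimental arm" counts as unacceptable.
- Experimental arm: 6 / 0.20 = 30. Control: 60 − 30 = 30. The plan's figures agree with each other, and one patient is 1/30 = 3.3 percentage points.

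**Effect on one arm's event rate**

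The documents give no adverse-event rate and no deviation rate, so the counts here are assumed: 3 of 30 patients with an event and 3 patients removed as major deviators, of whom e had the event.

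Rate after exclusion = (3 − e) / (30 − 3)

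| Removed patients with the event (e) | Analysed rate | Rate in all treated |
|---|---|---|
| 0 | 3/27 = 11.1% | 3/30 = 10.0% |
| 1 | 2/27 = 7.4% | 10.0% |
| 2 | 1/27 = 3.7% | 10.0% |
| 3 | 0/27 = 0% | 10.0% |

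**Effect on the difference between arms**

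All exclusions are taken from the experimental arm, and control stays at 3/30 = 10.0%. Differences are experimental minus control.

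- Experimental arm 3/30 before exclusion, difference 0. After removing 3 patients the difference runs from 11.1 − 10.0 = +1.1 points (no events removed) to 0 − 10.0 = −10.0 points (all 3 events removed).
- Experimental arm 6/30 = 20.0% before exclusion, difference +10.0 points. After removing 3 patients with 0, 1, 2 or 3 events, the rates are 6/27 = 22.2%, 5/27 = 18.5%, 4/27 = 14.8% and 3/27 = 11.1%. The differences are +12.2, +8.5, +4.8 and +1.1 points.

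The shift can go either way. It is larger downward in these examples because each removed event takes one from a small numerator.

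**The case against.** The strongest objection is that stopping treatment because of a side effect follows the protocol. Section 6.3 provides for permanent suspension after grade 4 toxicity judged directly related to the study treatment. Sections 6.6 and 7.3 list a possibly related serious event, the patient's wish and medical decision among the grounds for ending treatment. A reader might infer that 11.7 empties the discontinuation component of endpoint 6 by removing the very patients it should count. The documents do not support that: a patient who stops under these rules has not deviated, and 11.7 does not remove that patient. This part of the objection stands. What remains is informal dose-skipping, unsanctioned schedule changes and missed visits.

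A reader might also infer that the exclusion must make treatment look better tolerated. That does not follow either. Removing event-free deviators raises the rate, as 3/27 = 11.1% against 3/30 = 10.0% shows.

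The problem may also be rare. Participants have been stable on this drug for two years (section 7.1), those whose adherence cannot be ensured are excluded (section 7.2), and section 4 expects no serious long-term side effects in most such patients. This limits the likely size but does not supply a safety population.

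Finally, 11.7 already conflicts with the intention-to-treat statement for the primary endpoint, so its reach over safety can be called an inference from silence. The conflict is real and can be resolved in the same edit. But settling it for the primary endpoint alone would still leave endpoint 6 with only 11.7 to govern it. Individual notification of serious events is unaffected throughout.

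**Conclusion.** The point holds as a gap that can bias the safety comparison. As written, events in patients classed as major deviators are recorded and notified but fall outside the analysis of endpoint 6. The classification has no definition, can be made with arm and event known, and rests on 7 compliance checks in one arm against 2 in the other.

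The size and direction of any bias cannot be derived from the documents. With 30 per arm (implied by the plan) and an assumed 3 patients with events, removing 3 deviators puts the reported rate anywhere from 0% to 11.1%, against 10.0% in all treated patients. That is a range of possibilities and not a forecast. The change should be made, because the rule as stated can give a worse answer and correcting it needs no new data.

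**What to change.** Add to section 11.7:

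> Secondary endpoint 6 and all adverse-event tables are analysed in every randomised patient who took at least one dose of study medication after randomisation, by allocated arm, with no exclusion for protocol deviations. Any deviation-free set is used only for a supplementary per-protocol analysis.

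Counting doses from randomisation avoids doubt about a first tablet taken on Day 0. Keeping patients in their allocated arm preserves the randomised comparison when someone changes schedule.

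The cost is this added text and slightly more analysis work. No new data, visits or patients are needed, since section 10 already has every event collected. The reported event rates may look less favourable.
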